### *IIIf Follow-Up Procedures*

Follow-up assessments will be auto-sent to participants at +17 days (2 weeks beyond initial mailing, accounting for ~ 3 day delay in mailing), +33 days (same delay), +2, +3 and +6 months. Participants are reimbursed for completion of each of five interviews at an escalating rate and with bonus for completion of all. We have excellent

history of participant retention across our prior studies. Spanning at least 5 trials, encompassing >10,000 participant phone contacts, we consistently complete 80-90%. In our prior study of NRT sampling in South Carolina, we completed 96% of all scheduled contacts, our best yet. Payments are sent after each completed assessment (gift card or code for online purchase), and again the procedures are well established. Participants will also be able to earn referral bonuses for referring friends and family who enroll in the study.

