### *III f Assessments*

All interview data are entered in real time within a REDCap database, ensuring high data quality. We have established assessment protocols for all outcomes. Our follow-up interview has been extensively used in our prior studies and is timed at ~20 minutes. Self-report data include the following:

Baseline questionnaire will ascertain basic demographics and smoking history, including measures of dependence,(88) prior use of medications, and all hypothesized mediators (\*listed below).

Smoking (Reduction) Using Timeline Follow Back (TLFB) methods, we assess cigarettes per day over the previous seven days, and from this can calculate abstinence (defined below), as well as smoking reduction, and percent who achieve 50% reduction. We also track use of other tobacco products, including e-cigarettes.

Abstinence is defined as both “floating” (any 7 day period of non-smoking) and point prevalence, as recommended for “cessation-induction” studies.(89) We will track longest duration of abstinence and relapse following stated quit attempts.

Quit Attempts We will track the incidence of any self-defined and “serious” quit attempts over the 3-month follow-up period. The latter is the typical measure of quit attempts, used in CDC reports, and is defined as an attempt lasting  $\geq 24$ hrs. We will also report on the maximum duration, and latency of each QA since baseline.

Use of varenicline, NRT other meds We will determine the incidence and frequency of medications used, both during the sampling period and beyond. For varenicline, we will assess actual dosage used as well as titration patterns, days of use, and whether or not the person “converted” to sustained use (when, how, through whom).

\*Self-Efficacy, Motivation, & Confidence to Quit We will use single item (0-10 visual analog scale) measures for each. Our ladders have adequate test-retest stability and predictive validity.(90)

\*Attitudes Towards varenicline, NRT Based largely on prior work in this area(58, 91), we have published(25, 75) on 1) positive, and 2) negative attitudes towards medications, as well as 3) general knowledge of them.

\*Treatment Self-Regulation Questionnaire The TSRQ(47) is a well-established measure of autonomous motivation; i.e., the degree to which decisions on quitting are self-determined and/or controlled by others.

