### *III g Electronic Diaries during Sampling*

All participants will be asked to complete a brief diary to assess smoking behavior and use of meds. These diaries, which will include brief mood assessments, provide additional, real-time risk monitoring, not to replace traditional adverse event assessment (above), but to complement. Our intent is to better capture day-to-day fluctuations in medication use and smoking. Each of our recent trials have used this diary approach, with excellent compliance (88% for one study, 83% for another). Diaries will assess cigarettes smoked per day, medications/products used, purposes of that use (to reduce/quit), and mood/affect. Diaries ( $\leq 2$  min each) will be electronically collected daily throughout the sampling period (28 days). We have established procedures to auto-send an email/text on a set schedule. Thus, per eligibility criteria above, we require participants to have smartphone capacity, and they will be compensated for compliance based on % diaries completed (e.g., \$100 for 90-100% compliance, \$70 for 75-90% compliance, etc.). There is some debate as to whether EMA/diary procedures alter behavior, but recent evidence suggests not,(95, 96) but even if so this is equal between groups.

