
### *IIIi Power Estimations and Data Analyses*

Power: Our three-fold focus on outcomes includes 1) uptake (usage, conversion), 2) consequences (quit attempts, abstinence), and 3) mechanisms of varenicline and NRT sampling. We power on the most stringent of these to determine sample size: point-prevalence abstinence at six months (Aim 2), and we do so based on primary comparison of varenicline vs. inactive (non-sampling) control; see rationale above. Based on our early work, and under our belief that varenicline sampling will result in marginally better outcomes than NRT (12-15% in our prior studies) we anticipate a quit rate of 18% in varenicline vs. 8% in control, the latter also in line with our prior studies. With 2:1 randomization for this comparison (VRN:control), and with power of 80%, this will require a total sample size of 413 participants across these two groups. We conservatively inflate this by 15% to account for potential attrition, though in past studies this was closer to 12%, thus resulting in 324 varenicline vs. 162 control participants. We secondarily add another, active comparator group of smokers receiving NRT sampling (n=162; 2:1:1 overall randomization), for a **total of 648 participants**. If we were to power on varenicline vs. NRT outcomes, this would require a total sample of 1300 VRN + 650 NRT (+ 160 possible control), and such a study would be infeasible within this mechanism, and likely infeasible within any R01, particularly given the costs of medication. With anticipated 324 varenicline vs. 162 NRT participants, we have 39% power to detect a difference of 18% vs. 12% in abstinence. We have been doing studies this large for some time and have great confidence in recruitment. Over a 48-month recruitment span (see Timeline below), we aim to recruit ~11/month. For our ongoing nationwide trial of e-cigarettes (eventual N=660), we've averaged ~25/month. Considering the recruitment process and minor time delays between consent and formal enrollment, it is difficult to stop at an exact number. Thus, we will enroll between 648-660 participants to abide by those at earlier steps of the process.

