Outcomes pertaining to uptake, usage and conversion (independent use of varenicline, NRT; Aim 1) are focused *within* each active treatment group individually, though we can compare each of these outcomes *between* medication groups as well, per binary/continuous analyses below. With 360 total participants in varenicline group, a two-sided 95% confidence interval will have a maximum half-width of 0.052 (e.g., 95% CI on an observed rate of 50% would range from 0.448 to 0.552). With 162 participants in NRT group, the maximum half-width for uptake parameters is .077. As the observed proportion deviates from 50% (either higher or lower), the 95% confidence interval will decrease in width, providing more precision on the estimate (e.g., 95% CI on 90% would range from 0.896 to 0.931 with n=324). A confidence interval as wide as +/- 5% is a relatively small width and one we are willing to accept for our estimates on uptake, and conversion. Formal mediation analyses (Aim 3: mechanisms of change, within and between groups) are not planned, but we can test whether the sampling intervention results

in greater change in mechanism variables (\*above) similarly vs. differently for varenicline vs. NRT. All analyses are based on an intent-to-treat approach and are nearly identical to analyses from our current and prior studies. Exploratory analysis will be performed on all variables to determine if transformations are needed. Any significant baseline differences between groups will be included in analyses. All analyses will be run separately for full intent-to-treat sample and those retained per protocol. We are specifically interested in whether sampling effects generalize to those who are and are not motivated to quit, and we will examine this via sensitivity (subgroup) analyses. We are under-powered for tests of treatment interactions.

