Missing Data & Dropout: The most conservative approach for handling missing data(100) is to substitute them with baseline values, assuming outcomes have all returned to baseline, with no quit attempts made or abstinence achieved. If this assumption is incorrect, it biases the results towards the null by reducing between group differences.(100) We expect few missing data and thus plan for this approach. If missing data >10%, we will calculate results using this conservative method but also using methods in which missing data are imputed as described in the SRNT guidelines, and will assess whether dropout differs by study group (not the case in our prior trials). Abstinence will be reported both with and without (missing samples) CO verification.

Feasibility and Measures of Uptake: Our ongoing proof-of-concept study provides an early sense of study feasibility and thus this is not a main outcome of the trial. Nonetheless, we will deem our approach feasible if: a) at least 80% of varenicline group tries the medication, b) with reasonable duration of use (e.g., median days of use  $\geq 14$  days), c) at least 50% of varenicline group self-titrates to 2mg, d) at least 30% convert to independent use, and e) <5% of adverse events from varenicline are serious.

Binary Outcomes (incidence rate of quit attempts & cessation; % treatment uptake/conversion) will first be examined over the entire study period from baseline to end of follow-up by calculating frequencies/percentages as well as 95% confidence intervals for each medication group. Chi-square tests (or Fisher's exact tests as needed) will compare groups on binary outcomes to determine if effects from sampling group exceed those from control group. Both the control group (primary/powerful comparison) and NRT group (secondary) will serve as referent for varenicline group outcomes. Covariates will be included where necessary based on baseline differences. All tests will be considered significant at the  $\alpha=0.05$  level of significance.

Continuous Outcomes (duration of abstinence, smoking reduction) measured over the entire study period from baseline to the end of follow-up will be evaluated using general linear modeling with a main effect of group to determine group differences. Covariates will be added as necessary to account for baseline group differences.

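### Counting missing participants as baseline does not always bias toward the null, and the checks that would show this are promised only above 10% missing data

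*Combined protocol and SAP*

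**What the plan says.** The Missing Data & Dropout paragraph of section IIIi sets missing outcomes to baseline, meaning no quit attempt and no abstinence, and calls this the most conservative approach. On the consequence of being wrong it states: "If this assumption is incorrect, it biases the results towards the null by reducing between group differences". No condition on dropout is attached.

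The next safeguard is conditional: "If missing data >10%, we will calculate results using this conservative method but also using methods in which missing data are imputed". The same sentence goes on to say that the team "will assess whether dropout differs by study group (not the case in our prior trials"), so as written the dropout comparison also depends on exceeding 10%. The plan does not say whether the 10% is pooled or per arm, or to which visit or outcome it applies.

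Other relevant statements:

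- Power paragraph, section IIIi: "We conservatively inflate this by 15% to account for potential attrition, though in past studies this was closer to 12"%.
- Section IIIf, Follow-Up Procedures: contact completion in past trials is usually 80-90%, and "In our prior study of NRT sampling in South Carolina, we completed 96% of all scheduled contacts, our best yet".
- Section IIIi, without condition: "All analyses will be run separately for full intent-to-treat sample and those retained per protocol".

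**The concern.** Whether baseline substitution is conservative depends on how dropout, and success among dropouts, compare between arms. The trigger measures only the total amount missing. Low but uneven missingness could therefore leave the main analysis labelled conservative while neither of the two planned checks is committed to.

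Imbalance is possible in this design. Control participants receive no medication and there is no placebo, so everyone knows whether a sample came. At stake is whether a modest result favouring varenicline, or one against it, could partly reflect who was lost.

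**Working it through.** **Inputs from section IIIi.** 324 varenicline and 162 control; anticipated six-month abstinence 18% vs 8%; alpha 0.05; 80% power; 15% attrition. The standard two-sided comparison of two proportions with 2:1 allocation gives 138 control and 414 in total, against the stated 413. Then 413/0.85 = 486 = 324 + 162. The plan's sample size is reproduced, so two-sided testing is used below.

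**Assumed, because the documents give no figure.** Dropout by arm, and success among dropouts. Let d be dropout and q true success among dropouts in an arm. Ranges run from q at half the arm's rate (k = 0.5) to q equal to it (k = 1).

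**Shift.** The observed rate in an arm is p − d·q, so the difference (varenicline V minus control C) moves by

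dC·qC − dV·qV.

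- No true effect and equal q in both arms: any imbalance creates a false difference, toward whichever arm loses fewer people.
- 18% vs 8% with q at the arm rates: the difference is overstated only if 0.08·dC > 0.18·dV, that is dC/dV > 0.18/0.08 = 2.25. The risk ratio rises with any excess control dropout.
- Equal dropout is not sufficient protection, because the shift is then d·(qC − qV). With d = 8%, qV = 4% and qC = 8%, it is 0.08 × 0.04 = +0.32 points.

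**Overall missingness in each scenario.** Control-heavy scenarios take NRT dropout equal to varenicline's; reverse scenarios take it equal to control's.

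- 5%/20% (V/C): (486 × 0.05 + 162 × 0.20)/648 = 8.75%. Over the two compared arms, (324 × 0.05 + 162 × 0.20)/486 = 10.0%.
- 2%/10%: (486 × 0.02 + 162 × 0.10)/648 = 4.0%, the level implied by 96% completion.
- 10%/2%: (324 × 0.10 + 324 × 0.02)/648 = 6.0%; two arms, 7.3%.
- 20%/5%: (324 × 0.20 + 324 × 0.05)/648 = 12.5%, so the checks would run.

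**No true effect, abstinence 8% in both arms.** Exact binomial enumeration of the uncorrected chi-square test, 324 vs 162:

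| Dropout V/C | Observed rates at k = 1 | Rejection, k = 0.5 to k = 1 | Part favouring the arm with less dropout |
|---|---|---|---|
| none | 8.0% vs 8.0% | 5.04% | V 2.24, C 2.80 |
| 5%/20% | 7.6% vs 6.4% | 5.29-6.91% | V 3.72-6.11 |
| 2%/10% | 7.84% vs 7.2% | 5.02-5.36% | V 2.94-3.85 |
| 10%/2% | 7.2% vs 7.84% | 5.40-6.16% | C 3.74-4.95 |
| 20%/5% | 6.4% vs 7.6% | 6.05-8.65% | C 4.79-7.99 |

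**Planned effect, 18% vs 8% (true difference 10.0 points, risk ratio 2.25).** The observed difference is 0.18(1 − k·dV) − 0.08(1 − k·dC):

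| Dropout V/C | Difference (points) | Risk ratio |
|---|---|---|
| 5%/20% | 10.35 (k = 0.5) to 10.70 (k = 1) | 2.44 to 2.67 |
| 2%/10% | 10.22 to 10.44 | 2.34 to 2.45 |
| 5%/10%, k = 1 | 9.90 | 2.38 |
| 10%/20%, k = 1 | 9.80 | 2.53 |
| 20%/5% | 8.40 to 6.80 | 2.08 to 1.89 |
| 15%/15%, k = 1 | 8.50 | 2.25 |

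The last four rows agree with the plan's sentence on the difference scale; the first two do not.

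**Quit attempts, no true effect, at 34% or 43%** (the two rates in NRT Sampling Study 1). Dropout of 5%/20% gives rejection of 8.6-10.3% at k = 0.5 and 20.7-28.0% at k = 1. Dropout of 2%/10% gives 5.9-6.4% and 9.1-11.0%. The k = 1 figures are upper bounds, because they treat every attempt among the missing as unrecorded.

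**The case against.** The best counter-argument is the retained-sample analysis, which is always run. If dropouts succeed at their arm's rate, that comparison is unbiased: under 5%/20% and no effect, the full-sample difference is +1.2 points and the retained difference 0.0. At half rate the two analyses bracket the truth: +0.6 and −0.8 points under no effect, 10.35 and 9.47 around a true 10.0. This is right, and it is a real partial safeguard. It depends on those assumptions about dropouts, the retained per-protocol set is not further defined, and it neither compares dropout between arms nor corrects the sentence.

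The gap also needs unusual conditions. Attrition of 12-15%, or completion of 80-90%, would usually meet the trigger; of the figures quoted, only the 96% study falls clearly below it. Prior trials showed no differential dropout. The 5%/20% scenario sits exactly at 10.0% over the two compared arms, and a per-arm reading would trigger the checks. These points stand and limit the weight of the concern. They do not justify making the check conditional in a new trial.

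Per-group percentages and two analysis sets should make uneven loss visible to a careful reader. That is likely, but it is not a commitment to assess it.

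For quit attempts, the plan tracks "quit attempts over the 3-month follow-up period" at several contacts, and diaries "will be electronically collected daily throughout the sampling period (28 days"), so many attempts by people later lost would already be recorded. At the first-month rates in NRT Sampling Study 3 (18-24%), 5%/20% dropout gives 6.4-7.1% rejection at half rate. The large upper bounds should not be read as expected values.

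**Conclusion.** The concern holds. The statement about direction is false without a condition on dropout and on success among dropouts, and the 10% trigger tests quantity when direction depends on imbalance.

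The consequence is modest. Below the threshold, false rejection for abstinence moves from 5.0% to at most 6.9% in the scenarios examined, and a true 10.0-point difference is overstated by at most 0.7 points. On the difference scale at the planned rates, the sentence still holds unless control dropout exceeds 2.25 times varenicline dropout, if dropouts succeed at their arm's rate. All sizes rest on assumed arm-specific dropout. The algebra does not. It should be changed because the correction is easy and is best committed to before results are known.

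**What to change.** - Keep missing = smoking as the main abstinence analysis.
- Replace the unconditional sentence with one saying that the direction of bias depends on dropout, and on success among dropouts, in each arm.
- Remove the 10% trigger, so that missingness by arm and the already planned imputation analysis are always reported. This also removes the need to define the base for the 10%.
- Optionally, add a tipping-point analysis that varies success among the missing separately by arm.

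The cost is a few lines of SAP wording and a modest amount of analysis. No new data are needed.

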**Figure of Study Flow for STARS**

Randomization, Stratification We recruit smokers wanting to quit ( $\geq 7$  on 0-10 scale) and not, and we use this as a stratification variable. We considered a number of other stratification variables (e.g. cigs/day, insurance status) but believe that randomization will adequately handle these. We will randomize participants to group in a 2:1:1 ratio, with intent to increase precision of our parameter estimates within the varenicline group (n=324), consistent with our intent to understand use patterns and uptake of varenicline.

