Mechanisms of Change: We hypothesize that varenicline sampling will enhance quit motivation & confidence, as well knowledge of and attitudes toward medication, autonomy to quit, and will decrease cessation fatigue. We will examine all through analyses of continuous outcomes above. It will be interesting to explore whether and how these non-pharmacologic mechanisms differ for varenicline vs. NRT. Medication expectancies, knowledge, and familiarization might differentially vary through varenicline/NRT sampling, as might motivation and confidence. Note that our focus is on non-pharmacologic mechanisms, since the pharmacologic mechanisms of both varenicline and NRT are well-established and also since our design does not include a placebo comparator. Also note that formal tests of mediation can be explored but we may not be powered for these.

Diary Analyses: Mixed effects regression models(101) will be used to model diary data outcomes (e.g., days of med use) to allow for repeated observations per participant as well as for time-invariant (group, gender, etc.) and time-varying covariates (e.g., motivation to quit). These types of models allow for the inclusion of incomplete data across time, so we can include all reported data, even if <28 days per ppt. Any results obtained from these mixed effects models will be considered exploratory and primarily used to gather information on effect sizes.

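### The motivation stratum and the baseline values are left out of the main models; adding them is a low-priority, nearly free gain in precision, not a correction of validity

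*Combined protocol and SAP*

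**What the plan says.** The Randomization, Stratification paragraph (under the study flow figure) splits smokers at 7 on a 0-10 scale of wanting to quit, "and we use this as a stratification variable". Other candidate strata were considered and left to randomisation. Amendment 16 dropped the equal-numbers quota but kept the stratification.

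Section IIIi sets the analyses:
- **Binary outcomes:** chi-square or Fisher tests between groups. On further terms: "Covariates will be included where necessary based on baseline differences".
- **Continuous outcomes:** these "will be evaluated using general linear modeling with a main effect of group to determine group differences". Here too, further terms are conditional: "Covariates will be added as necessary to account for baseline group differences".
- **The mediators** go through the same model: "We will examine all through analyses of continuous outcomes above".
- **General rule:** "Any significant baseline differences between groups will be included in analyses".

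Motivation appears in two other places in IIIi. One is the question whether effects hold in motivated and unmotivated smokers, where "we will examine this via sensitivity (subgroup) analyses". The other is as an example covariate in the diary mixed models, which are labelled exploratory. Neither puts the stratum into a main comparison.

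The Assessments section has all hypothesised mediators measured at baseline. For Aim 3 the plan looks for "greater change in mechanism variables", without defining the estimator.

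**The concern.** A factor used to stratify the randomisation is normally carried into the analysis, and a continuous outcome measured at baseline is normally adjusted for that value. The plan commits to neither. Its only route to adjustment is an observed baseline difference. The stratum is balanced by design and so will hardly ever qualify. Any other variable qualifies because of chance imbalance, not because it predicts the outcome. The rule also has no variable list, and it is worded three ways, only one of which mentions significance.

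Mechanisms are one of the three primary aims, and what is at stake is mainly the width of the intervals for those and other continuous outcomes. A smaller matter is that the reported model is not fixed in advance in a trial without placebo.

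**Working it through.** **1. The plan's own figures.** Inputs from the Power paragraph: 8% vs 18%, 2:1 allocation, 80% power, alpha 0.05 (two-sided reproduces the figure). The pooled rate is (0.08 + 2×0.18)/3 = 0.1467. The control-arm n is

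[1.96·√(0.1467×0.8533×1.5) + 0.842·√(0.08×0.92 + 0.18×0.82/2)]² / 0.10² = 137.4.

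The total is 3 × 137.4 = 412.3, which rounds up to the stated 413. Then 413/0.85 = 486 = 324 + 162. The stated 39% for 18% vs 12% also reproduces (39.2%). The sample size is sound and does not depend on this point.

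**2. Abstinence with and without the stratum.** Simulation used 400,000 trials per setting, arms balanced within stratum, and a common treatment odds ratio of (0.18/0.82)/(0.08/0.92) = 2.52. The strength of the stratum is not in the documents, so its odds ratio is varied. At 324 vs 162 with a 50:50 stratum split:

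| Stratum OR | Chi-square power | Stratified (CMH) power |
|---|---|---|
| 1 | 87.4% | 87.3% |
| 2 | 86.5% | 86.6% |
| 3 | 85.3% | 85.8% |
| 4 | 84.4% | 85.2% |

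At N = 413 the change runs from -0.3 to +1.2 points. If 70% are motivated (N = 486), it is within ±0.1. The type I error of the planned chi-square for abstinence is 4.7-5.1%.

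**3. What the covariate rule does.** With 2:1:1 permuted blocks (block sizes assumed) it selected the stratum in 0 of 3,000 trials per block size. The Assessments section yields ten baseline mediators: self-efficacy, motivation, confidence, positive attitudes, negative attitudes, knowledge, autonomy, cessation fatigue, expectancies and self-control. With motivation balanced by stratification (a median split is assumed), nine remain free. If they are uncorrelated, at least one is significant in about 1 - 0.95⁹ = 37% of trials. At mutual correlation 0.5 this falls to about 20%. Applied mechanically at p < 0.05, the rule has size 3.3-4.8% for continuous outcomes. At baseline correlation r = 0.5 and a 0.2 SD difference it has 55% power, against 66% for always adjusting.

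**4. Continuous and mechanism outcomes.** For a unit-SD outcome the variance factors are 1 (follow-up only), 2(1 - r) (change score) and 1 - r² (ANCOVA). The standard error is √factor × √(1/162 + 1/324) = √factor × 0.0962. Power is Φ(0.2/SE - 1.96) for an assumed 0.2 SD difference. At r = 0.5, for example:
- Change score: Φ(0.2/0.0962 - 1.96) = 55%.
- ANCOVA: Φ(0.2/0.0833 - 1.96) = 67%.

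| r (assumed) | Follow-up only | Change score | ANCOVA |
|---|---|---|---|
| 0.3, complete data | 55% | 42% | 59% |
| 0.5, complete data | 55% | 55% | 67% |
| 0.7, complete data | 55% | 77% | 83% |
| 0.3, 15% replaced by baseline | 42.5% | 36.6% | 48.8% |
| 0.5, 15% replaced by baseline | 42.3% | 48.3% | 57.7% |
| 0.7, 15% replaced by baseline | 42.0% | 69.4% | 75.1% |

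The last three rows are simulated, with missingness completely at random and the plan's baseline substitution. Over 12-15% replaced (the attrition figures in the Power paragraph), ANCOVA gains about 6 to 13 points over a change score and 6 to 33 over follow-up only. With complete data at r = 0.5 the 95% half-width falls from 1.96 × 0.0962 = 0.189 to 1.96 × 0.0833 = 0.163 SD, about 13%.

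**5. At the effect sizes in the Preliminary Studies.** For d = .42 and .46 (NRT Sampling Study 1) with 15% replaced, change-score power is 98.0% and 99.2%. There the benefit is only a narrower interval.

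**The case against.** The strongest reply is that little is at risk. The one powered endpoint gains about a point at best and can lose a fraction of one, and at the mechanism effects seen earlier by this group power is already near its ceiling. That stands, and it sets the low priority.

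A second reply is that follow-up only is a straw man. The plan speaks of change, says its analyses are nearly identical to those of prior studies, and tabulates the earlier mechanism results as pre-to-post changes. That also stands: the change score is the natural comparator, and the 6-33 point range belongs to the less likely reading.

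A third reply is that the gain rests on an assumed effect and assumed correlations, so only a range can be given. In addition, both attrition settings exceed 10%. At that level the plan also calls for an imputed analysis, which was not modelled here. Both points are fair.

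Four stronger readings are tempting, and the documents do not support them:
- **That omitting the stratum invalidates the test or the sample size.** The planned test is nominal or slightly conservative, and 413 reproduces.
- **That the covariate rule inflates false positives.** Used mechanically it is conservative. Size reaches 6.4-8.5% for continuous outcomes only if the smaller of the adjusted and unadjusted p-values is reported, which the plan nowhere proposes.
- **That motivation is known to predict abstinence.** NRT Sampling Study 2 links it to quit attempts but says it is not needed for quitting success.
- **That motivation is ignored.** It has the subgroup and exploratory diary roles described above.

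**Conclusion.** The point holds as a low-severity improvement in efficiency and pre-specification. The stratum and the baseline values are collected but enter no main model, and the baseline-difference rule does not make up for this. The change in abstinence power is about -0.3 to +1.2 points for stratum odds ratios of 1 to 4. For outcomes with a baseline value, ANCOVA gains about 6 to 13 points over a change score at 0.2 SD with 12-15% replaced. That rests on r between 0.3 and 0.7, which the documents do not give. Power gains matter only for modest differences, which may include the secondary varenicline vs NRT contrast (same arm sizes). Elsewhere the return is precision and a model fixed in advance.

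**What to change.** Before outcomes are examined by arm, pre-specify:

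1. **Binary outcomes:** the Cochran-Mantel-Haenszel test stratified by motivation, in its exact version where counts are sparse, with a stratum-standardised risk difference.
2. **Continuous and mechanism outcomes:** ANCOVA with that outcome's own baseline value where one exists, plus the motivation stratum. Use the stratum only for duration of abstinence, which has no baseline value.
3. **Covariate rule:** delete the wording that adds covariates because of baseline differences, in all three places.

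Amendment 29 (September 2024) raised the enrolment ceiling, which suggests that recruitment was far advanced, and the documents do not show whether outcomes by arm have been seen. If they have, keep the planned tests as primary and label the adjusted analyses as added later.

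The cost is wording only, since no new participants or data are needed. The downside is up to about 0.3 points of power for abstinence if the stratum turns out not to be prognostic.
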